13 METHODS OF EFFICACY ANALYSES

13.1 Primary Efficacy Analysis

The primary endpoint is the change from Baseline to Week 8 in the HAMD-17 total score. The primary analysis will be based on the Full Analysis Set.

The null and alternative hypotheses for the primary endpoint are as follows:

Let Δ be the mean change from Baseline to Week 8 in the HAMD-17 total score:

The null hypothesis for the primary efficacy endpoint is: $\Delta = 0$

The alternative hypothesis for the primary efficacy endpoint is: $\Delta \neq 0$

13.1.1 Primary Analysis using MMRM in the Full Analysis Set

The HAMD-17 total score will be analyzed using mixed model repeated measures (MMRM) in the Full Analysis Set. The dependent variable will be the change from Baseline in the

HAMD-17 total score. The independent variables in the model will include the following: visit (Week 2, Week 4, Week 6, and Week 8), Baseline-by-visit interaction, and the Baseline HAMD-17 total score as a continuous covariate. An unstructured covariance matrix will be used and the Kenward-Roger approximation will be used to adjust the denominator degrees of freedom. Least squares (LS) adjusted means will be estimated using observed cases (OC).

In the event that the model fails to converge using the unstructured covariance matrix, then the following covariance structures will be modeled in the order given: heterogeneous Toeplitz, heterogeneous compound symmetry, heterogeneous autoregressive(1), Toeplitz, compound symmetry, autoregressive(1), variance components. The first covariance structure that allows for convergence will be selected for the final model.

Summary statistics for the HAMD-17 total score (observed and change from Baseline) will be presented for all visits from Baseline through Week 8. For change from Baseline values at each post-Baseline visit, LS means and standard errors (SE), the corresponding 95% confidence interval and p-value will also be presented. In addition, LS mean \pm SE over time for the change from Baseline values will also be presented in line plots.

The hypothesis testing will be performed based on the LS mean change at Week 8 and will be tested at an alpha level of 0.05 (2-sided).

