### 9.8.1 Primary Efficacy Analyses

The primary efficacy endpoint is the change from Baseline to Week 8 in the HAMD-17 total score. The primary analysis will be based on the FAS.

The null and alternative hypotheses for the primary endpoint are as follows:

- The null hypothesis is that the mean change from Baseline to Week 8 in HAMD-17 total score is equal to 0.
- The alternative hypothesis is that the mean change from Baseline to Week 8 in HAMD-17 total score is not equal to 0.

The HAMD-17 total score will be analyzed using the mixed model repeated measures (MMRM). The dependent variable will be the change from Baseline in the HAMD-17 total score, and the independent variables will include the following: Baseline HAMD-17 total score, visit (Weeks 2, 4, 6, and 8), and Baseline HAMD-17 total score-by-visit interaction. An unstructured covariance matrix will be used to model the within-subject errors, and the Kenward-Roger approximation will be used to adjust the denominator degrees of freedom.

The treatment effect for the primary endpoint will be estimated as the least-squares mean change from Baseline to Week 8, and will be tested at a significance level of 0.05. In addition, the treatment effect will also be estimated at each of the other time points (Weeks 2, 4, and 6) using the same MMRM, and will be considered secondary endpoints.

In addition, a paired t-test using a last observation carried forward (LOCF) imputation method will be performed at each post-baseline visit.

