3.5 Determination of Sample Size

The initial sample size calculation was based on a standard deviation of 8.0 and a dropout rate of 10%. An interim review of the statistical assumptions was conducted after 9 subjects completed the Week 8 visit, and the sample size was recalculated. The standard deviation in HAMD-17 total score change from Baseline to Week 8 was observed to be lower, and the dropout rate higher, than the initial assumptions. Therefore, the sample size has been recalculated as follows.

Assuming the standard deviation for the change in HAMD-17 total score from Baseline to Week 8 is 6.0 points, 34 evaluable subjects will provide 80% power to detect a minimum mean reduction of 3 points from Baseline to Week 8 at a significance level of 0.05 using a 2-sided paired t-test.

Adjusting for a potential non-evaluable rate of up to 15%, approximately 40 subjects will be enrolled.

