12.5 Examination of Subgroups

The MMRM analysis described in Section 13.1.1 will be performed separately for the primary efficacy variable (HAMD-17 total score), and for CGI-S and CGI-I as described in [Section 13.1.6](#) and [Section 13.1.7](#), respectively, for each of the following subgroups:

- treatment regimen (pimavanserin monotherapy or pimavanserin adjunctive therapy)
- age group (<70 or \geq 70 years old)
- sex (male or female)
- primary race (white or non-white)
- Baseline symptom severity measured by HAMD-17 total score (<24 or \geq 24)

The LS mean changes with corresponding 95% CIs from the subgroups will also be graphically presented in forest plots for the above efficacy variables.

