13.1.2 LOCF Paired T-test for HAMD-17

A paired t-test using LOCF will be performed on the HAMD-17 total score change from Baseline at each post-baseline visit using the Full Analysis Set. Summary statistics for the HAMD-17 total score (observed and change from Baseline) will be presented for all visits from Baseline through Week 8. For change from Baseline values at each post-Baseline visit, 95% confidence intervals and p-values will be presented.

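### The primary one-arm LS-mean test treats the sample mean baseline as known, so its actual alpha exceeds 0.05 whenever baseline and change are correlated

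*SAP*

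**What the plan says.** Protocol 9.8.1 states the hypothesis without conditioning on baseline: "The null hypothesis is that the mean change from Baseline to Week 8 in HAMD-17 total score is equal to 0". SAP 13.1 does the same, defining Δ to "be the mean change from Baseline to Week 8 in the HAMD-17 total score" and testing Δ = 0. SAP 3.1 describes a single-arm study.

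The test itself is in SAP 13.1.1. Change from baseline is modelled on visit, "Baseline-by-visit interaction, and the Baseline HAMD-17 total score as a continuous covariate", with unstructured covariance and Kenward-Roger degrees of freedom. Then: "The hypothesis testing will be performed based on the LS mean change at Week 8", two-sided at 0.05. Neither document says at which baseline value the LS mean is evaluated.

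Three other passages bear on the point:

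- SAP 13.1.2 adds a supportive analysis: "A paired t-test using LOCF will be performed on the HAMD-17 total score change from Baseline at each post-baseline visit".
- SAP 3.5 sizes the trial "at a significance level of 0.05 using a 2-sided paired t-test", not on the MMRM.
- SAP 12.5 repeats the MMRM within subgroups: "The LS mean changes with corresponding 95% CIs from the subgroups will also be graphically presented in forest plots".

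**The concern.** In a two-arm trial, adjusting for baseline is harmless in this respect. Both LS means are evaluated at the same baseline with a common slope, so error in the mean baseline largely drops out of the difference.

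Here the estimate is a single mean, and nothing cancels. The sample mean baseline varies from trial to trial. If change depends on baseline, the LS mean varies with it. The MMRM standard error is conditional on the observed baselines and leaves this variation out. Kenward-Roger works conditionally on the same covariates, so it does not put it back.

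The error runs one way: for either sign of r, the p-value is too small and the interval too narrow. At stake is the level of the primary test, which both documents put at 0.05, and the width of its 95% CI. Weeks 2, 4 and 6 come from the same model. The same mechanism applies to the other change-from-baseline MMRMs and to the HAMD-17 and CGI-S subgroup intervals, though its size there is not known.

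**Working it through.** **Inputs from the documents.** SD of change 6.0, detectable mean reduction 3 points, 34 evaluable, about 40 enrolled allowing for 15% non-evaluable, two-sided 0.05 (SAP 3.5).

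**Assumed.** The LS mean is taken at the sample mean baseline. The documents give no baseline HAMD-17 SD, slope or r, so results are shown over a range of r.

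**1. The plan's own figure.** Noncentral t, n = 34, mean change 3, SD 6: power 80.8% (79.5% at n = 33). 34/0.85 = 40. The stated sample size reproduces. It rests on a paired t-test, whose standard error carries the full variance of the change.

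**2. The omitted term.** With complete data the unstructured MMRM gives the same Week 8 result as a regression of Week 8 change on baseline. At the sample mean baseline, the LS mean is the raw mean change.

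- True variance: SD²/n = 36/34 = 1.059, so SE 1.029.
- Variance estimated by the model: SD²(1−r²)/n. At |r| = 0.4 this is 36 × 0.84/34 = 0.889, so SE 0.943.
- Difference: slope² × baseline variance / n = r² × SD²/n = 0.16 × 36/34 = 0.169.
- Ratio of SEs: 0.943/1.029 = 0.917 = √(1−0.16).

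**3. Actual alpha.** Alpha = 2·P(t₃₂ > t₀.₉₇₅,₃₂ × √(1−r²)). The half-widths are simulated means; the paired t-test gives 2.08 points.

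| \|r\| | SE ratio | Actual alpha | Mean 95% CI half-width (points) |
|---|---|---|---|
| 0 | 1.000 | 5.0% | – |
| 0.1 | 0.995 | 5.1% | – |
| 0.2 | 0.980 | 5.5% | 2.04 |
| 0.3 | 0.954 | 6.1% | 1.98 |
| 0.4 | 0.917 | 7.1% | 1.91 |
| 0.5 | 0.866 | 8.7% | 1.80 |

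Simulation of the complete-data case agreed within about 0.2 points, including with baseline truncated at the entry threshold of 15. The paired t-test on the same data stayed at about 5%.

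**4. What r might be.** Hold the SD of change at 6.0. Assume baseline SD 3, 4 or 5 and Baseline–Week 8 correlation ρ of 0.3, 0.4, 0.5, 0.6 or 0.7. Solve for the Week 8 SD; then r = (ρ × SD_Week8 − SD_Baseline)/6. For example, baseline SD 5 and ρ = 0.3 give Week 8 SD 5.14 and r = (1.54 − 5)/6 = −0.58. Over the 15 combinations r runs from −0.58 to +0.40. Taking alpha = 2(1−Φ(1.96√(1−r²))), 7 give 5.1% to 5.4%, 4 give 5.6% to 6.0%, and 4 give 6.9%, 7.2%, 7.9% and 10.9%.

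**5. With dropout.** Two simulations used a four-visit unstructured REML MMRM, 40 enrolled and about 15% missing at Week 8, with (Week 8 completers − 2) degrees of freedom in place of Kenward-Roger.

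- Dropout depending on the last observed change: 5.5% at r = 0; 5.1%, 5.9%, 7.2% and 8.2% at r = −0.2, −0.3, −0.4 and −0.5; 6.8% at r = +0.4 (Monte Carlo SE 0.4 to 0.5 points).
- Dropout unrelated to outcome: 4.2% at r = 0; 5.4%, 7.2% and 9.0% at |r| = 0.2, 0.4 and 0.5 (Monte Carlo SE 0.5 to 0.8 points).

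**The case against.** The strongest reply is that the test is valid conditional on the baselines observed. That is true, but neither document states a conditional null; both refer to the mean change, without qualification. Either the null or the standard error has to change.

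Second, no excess is demonstrated for this trial. At r = 0 there is none, 11 of the 15 assumed combinations give 6.0% or less, and the 10.9% is one corner of the grid. This stands, and it is why the size is stated conditionally.

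Third, an unaffected paired t-test is already planned. The plan's tables would also reveal the problem: SAP 13.1.1 and 5.1.1 require the SE of the observed change beside the LS-mean SE, and their ratio is roughly √(1−r²). So a reader of the results could diagnose it, though a reader of the plan cannot. But the paired t-test is supportive and uses LOCF. If the two analyses disagree, the SAP makes the understated SE decisive.

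Fourth, the practical effect is modest unless r is large. In simulation at n = 34 with a true 3-point change, the planned test and the paired t-test reached different conclusions in about 1.6% of trials at |r| = 0.2 and 4% at 0.4. With a 5-point change and |r| no larger than 0.4, the figure was about 0.1%.

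Finally, the dropout simulations cannot resolve effects below about |r| = 0.3, and neither used Kenward-Roger itself. Both limits stand.

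**Conclusion.** The concern holds. For the null that the documents state, the planned Week 8 standard error is too small whenever r is not zero. The excess in alpha is about half a point or less at |r| up to 0.2, about one point at 0.3, two at 0.4 and nearly four at 0.5. This rests on the LS mean being taken at the sample mean baseline, and on a value of r that the documents do not supply. The mechanism is certain; its size in this trial is not. The sample size and power statement is unaffected, and with complete data so is the point estimate. The correction is worth making before the analysis: it costs little if r is small, and if r is large it avoids reporting a 7% to 9% test as a 5% test.

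**What to change.** Keep the planned MMRM. State in SAP 13.1.1 that the LS mean is evaluated at the Full Analysis Set mean baseline, and add (fitted Week 8 baseline slope)² × baseline variance / n to its variance, with n the number of Full Analysis Set subjects. In simulation the corrected test had alpha of 4.6% to 4.8% with complete data and 4.1% to 5.3% with 15% dropout. Apply the same correction at Weeks 2, 4 and 6, to the other change-from-baseline MMRMs and to the HAMD-17 and CGI-S subgroup intervals.

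An alternative is to put Baseline in the response vector, with visit as the only fixed effect and unstructured covariance, and to test Week 8 minus Baseline. The covariance fallback list in SAP 13.1.1 would then need replacing by structures that keep a separate Baseline variance and covariance. For example, take assumed baseline SD 3.6, later SD 6, and correlations 0.3 with Baseline and 0.7 between later visits. The Week 8 minus Baseline difference has variance 36, and differences between later visits have variance 21.6. Compound symmetry pools these to (4 × 36 + 6 × 21.6)/10 = 27.36, so alpha is 2(1−Φ(1.96√(27.36/36))), about 8.75%.

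The cost is SAP wording and a short programming change, with no new data. Intervals widen by about 2%, 5%, 9% and 15% at |r| = 0.2, 0.3, 0.4 and 0.5, and with complete data the corrected test is slightly conservative.

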13.1.2 LOCF Paired T-test for HAMD-17

A paired t-test using LOCF will be performed on the HAMD-17 total score change from Baseline at each post-baseline visit using the Full Analysis Set. Summary statistics for the HAMD-17 total score (observed and change from Baseline) will be presented for all visits from Baseline through Week 8. For change from Baseline values at each post-Baseline visit, 95% confidence intervals and p-values will be presented.

13.1.3 Secondary Efficacy Analyses

The Full Analysis Set will be used for all secondary efficacy analyses.

13.1.4 Change from Baseline to Weeks 2, 4, and 6 in HAMD-17 Total Score

See [Section 13.1.1](#) for details of this analysis.

13.1.5 HAMD-17 Responder Analysis

For the HAMD-17 total score, a treatment response is defined as a $\geq 50\%$ reduction from Baseline.

At each timepoint the proportion of responders will be descriptively summarized including 95% confidence intervals. Both OC, in which subjects with missing values at a given visit are excluded, as well as missing values imputed as non-responders will be presented.

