- ^e Applicable only to women of childbearing potential. A serum pregnancy test is performed at Screening and a urine pregnancy test at Baseline and Week 8.
- ^f Only weight will be measured after Screening.
- ^g Subject terminating early should at a minimum complete assessments of safety (vital signs, ECG, AEs, clinical laboratories, C-SSRS) and, if possible, complete all Week 8 assessments.

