4.2 Full Analysis Set

The Full Analysis Set will consist of a subset of subjects in the Safety Analysis Set who have both a Baseline value and at least one post-Baseline value for the HAMD-17 total score.

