5.3.1 Unscheduled Assessments

Both scheduled and unscheduled assessments, including the assessments at ET visits, will be considered for planned timepoint analyses. All assessments will be presented in data listings.

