12 EFFICACY ANALYSES

All efficacy analyses will be performed on the Full Analysis Set.

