12.3 Handling of Missing Data

Total scores that are missing, after any imputation of individual missing items as described in [Section 5.2.1](#), will not be imputed. Analysis of covariance (ANCOVA) and EQ-5D categorical analyses will be performed using the last observation carried forward (LOCF) method of imputation for missing data. The LOCF method will carry forward the Baseline value if necessary.

If the last dose date of study drug is missing for a subject who completed or early terminated from the study, then the date of the end-of-study/early termination visit will be used in the calculation of treatment duration. For the incomplete last dose date of the study drug, the imputation algorithms will be detailed in the ADS document. The missing or incomplete

dates will be displayed in the data listings as reported on the eCRF rather than the imputed dates.

For any data summarization that occurs before final database lock, if a subject is still ongoing, then that subject's last dose date will be imputed using the database extract date.

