13.1.7 CGI-I

The CGI-I score at each post-Baseline timepoint will be analyzed using an MMRM model similar to that used for the primary efficacy endpoint. The dependent variable will be the CGI-I score, and the independent variables in the model will include the following: visit (Weeks 2, 4, 6, and 8), Baseline CGI-S score (continuous covariate), and Baseline CGI-S score-by-visit interaction.

The CGI-I scores will also be dichotomized by combining scores of 1 or 2 (very much improved or much improved) into an “Improved” category, and all remaining scores into a “Not Improved” category. At each timepoint, the proportion of responders (very much improved or much improved) will be descriptively summarized including 95% confidence intervals. Both OC, in which subjects with missing values at a given visit are excluded, as well as missing values imputed as not improved, will be presented.

The observed (un-dichotomized) scores, as well as dichotomized scores, will be descriptively summarized by visit.

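### Minor: the HAMD-17 missing-as-non-responder rate omits any treated subject with no post-Baseline HAMD-17 total; add the same rate on the Safety Analysis Set

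*SAP*

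**What the plan says.** SAP 13.1.5 defines response as a fall of at least 50% from Baseline in the HAMD-17 total. At each timepoint it gives the proportion with a 95% CI on observed cases, "as well as missing values imputed as non-responders will be presented". SAP 13.1.7 treats the dichotomized CGI-I the same way: "as well as missing values imputed as not improved, will be presented". Neither section names a denominator of its own.

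The denominator comes from the general rules. SAP 12: "All efficacy analyses will be performed on the Full Analysis Set". SAP 13.1.3: "The Full Analysis Set will be used for all secondary efficacy analyses". SAP 4.2 limits the FAS to Safety Analysis Set subjects "who have both a Baseline value and at least one post-Baseline value for the HAMD-17 total score". Protocol 9.7.1 defines the FAS in the same way and uses it for all efficacy endpoints, and protocol 9.8.2 has the same missing-data rule for the responder rate. The Safety Analysis Set (SAP 4.1) needs only one dose of pimavanserin.

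The imputation rule in SAP 12.3 does not reach these rates: "Analysis of covariance (ANCOVA) and EQ-5D categorical analyses will be performed using the last observation carried forward (LOCF) method of imputation for missing data".

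**The concern.** A missing-as-non-responder rate is normally read as the cautious companion to the observed-case rate. Here it is cautious only about subjects who have at least one post-Baseline total. A subject who takes the drug and is lost before any usable rating, the earliest kind of loss, is in neither numerator nor denominator. For HAMD-17 such a subject cannot be an observed responder, so leaving the subject out can only raise the rate, or leave it unchanged if there are no responders.

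The study has one arm, so no comparator rate absorbs the shift; readers will see the absolute proportion. What is at stake is a descriptive secondary figure and its interval. The secondary objectives are exploratory (SAP 2.2), and no test or decision is attached to the rate.

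**Working it through.** **1. The plan's own figure.** Inputs from SAP 3.5: SD 6.0, mean reduction 3, two-sided 0.05, 80% power, 34 evaluable, up to 15% non-evaluable, about 40 enrolled.
- Normal approximation: ((1.960 + 0.842) × 6/3)² = 31.4, so 32.
- Noncentral t: power is 79.5% at n=33 and 80.8% at n=34, so 34 is reproduced.
- 34/0.85 = 40, also reproduced.

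This is used below only as the source of N=40, assuming that all enrolled subjects are treated. The documents give no figure for the response rate or for k.

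**2. Who can be left out.** Several rules keep the group small:
- A rating from Study Day 2 onward falls in the Week 2 window or a later one (SAP Table 2).
- Early-termination and unscheduled ratings count. SAP 5.3.1: "Both scheduled and unscheduled assessments, including the assessments at ET visits, will be considered for planned timepoint analyses".
- Up to three missing HAMD-17 items are imputed (SAP 5.2.1).
- Protocol section 4 asks for the end-of-treatment evaluations at withdrawal.

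The group is not ruled out. Note g to the schedule in SAP 3.2 says of anyone who stops before Week 8 that they "should at a minimum complete assessments of safety (vital signs, ECG, AEs, clinical laboratories, C-SSRS) and, if possible, complete all Week 8 assessments". HAMD-17 is not in that minimum.

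**3. Formula.** Let r be the responders, N the treated subjects, and k the treated subjects with no post-Baseline HAMD-17 total.
- All-treated rate, missing as failure: r/N
- FAS rate, missing as failure: r/(N-k)
- Ratio: N/(N-k)
- Difference: (r/N) × k/(N-k)

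**4. Numbers.** N=40; r and k are assumed. The ratio is 40/39 = 1.026 at k=1 and 40/38 = 1.053 at k=2. Intervals are exact (Clopper-Pearson) 95%.

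| r | k=0 (all treated) | FAS, k=1 | FAS, k=2 |
|---|---|---|---|
| 10 | 25.0% (12.7 to 41.2) | 25.6% (13.0 to 42.1), +0.64 | 26.3% (13.4 to 43.1), +1.32 |
| 16 | 40.0% (24.9 to 56.7) | 41.0% (25.6 to 57.9), +1.03 | 42.1% (26.3 to 59.2), +2.11 |
| 24 | 60.0% (43.3 to 75.1) | 61.5% (44.6 to 76.6), +1.54 | 63.2% (46.0 to 78.2), +3.16 |

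The range for k=1 to 2 is thus 0.6 to 3.2 points, against intervals about 28 to 33 points wide. Widening the assumed all-treated rate to 20% and 70% moves the ends to 0.51 (k=1) and 3.68 (k=2).

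**5. Is k=1 to 2 reasonable?** Protocol 1.3.2 describes an earlier study with 90 subjects randomized to pimavanserin and 87 in its FAS. 3/90 = 3.3%, and 3.3% of 40 is about 1.3. The adverse-event percentages quoted there fit a denominator of 90 (23.3% = 21/90, 22.2% = 20/90, 21.1% = 19/90), so all 90 were probably treated. Its responder table (protocol Table 1-1) is also on the FAS with missing as nonresponder. The 50.6% for at least 50% improvement fits 44/87; over 90 it would be 44/90 = 48.9%, or 1.7 points lower. This is only an indication: the population differs, that study's FAS definition is not given, and the counts are inferred from percentages.

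**6. CGI-I.** A subject without a post-Baseline HAMD-17 total may still have a CGI-I score, so the factor does not apply. With 16 improved in the FAS and k=1, the FAS rate is 16/39 = 41.0%. The all-treated rate is 16/40 = 40.0% if the excluded subject is not improved or has no score, and 17/40 = 42.5% if improved. The FAS rate could be 1.0 point higher or 1.5 points lower.

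**The case against.** The best defence is that nothing here is an error. Protocol and SAP agree on the FAS, on its use for efficacy and on the missing-data rule. No passage calls the imputed rate conservative or all-treated, and the sponsor reported an earlier study in the same way. The shift may be zero and is small against the interval. Analysis-set counts, a listing of FAS exclusions with reasons (SAP 6) and listings of all data (SAP 5) let a reader rebuild the all-treated HAMD-17 rate by hand. All of that stands, and it is why the point is minor. What remains is that the planned table and its CI would not show that rate.

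A reader might infer more than the documents support:
- *That dropouts in general escape.* They do not. A subject with any post-Baseline total stays in the FAS and counts as a failure at later missing visits.
- *That the response rate is overstated against the truth.* Unknown. The direction is fixed only relative to the all-treated rate with missing as failure.
- *That the whole 15% allowance is at risk.* At k=6 the gap would be 4.4 to 10.6 points for the same assumed rates, but SAP 3.5 does not define non-evaluable as having no post-Baseline total.
- *That the CGI-I rate is biased upward.* No direction can be claimed.
- *That the FAS rate should be replaced.* That would create an avoidable departure from protocol 9.7.1. The observed-case and imputed rates would then come from different populations, mixing the missing-data rule with the analysis set.

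One limit on the check: the text of protocol 9.3, on dropouts and missing data, does not appear in the public copy, and table specifications are held in separate documents (SAP 1). Some of the labelling may already be in place.

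**Conclusion.** The point holds as a minor, inexpensive improvement for HAMD-17. As written, the missing-as-non-responder rate excludes treated subjects with no post-Baseline total, and it exceeds the all-treated rate by the factor N/(N-k). The size rests on three assumptions: 40 treated, k of 1 or 2, and an all-treated response rate of 25% to 60%. On these the excess is 0.6 to 3.2 points; if k=0 it is nil. It is a choice of analysis set, not a contradiction, and it leaves the primary analysis and the sample size untouched.

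**What to change.** In SAP 13.1.5, keep both planned FAS rates (observed cases and imputed). Add the missing-as-non-responder rate with its 95% CI on the Safety Analysis Set, counting every treated subject without the needed value as a non-responder. Present the added rate as the conservative estimate, say that it supplements the FAS rule in SAP 12 and 13.1.3, and label the analysis set and N on each row. Note the addition in SAP 18, which now reads as not applicable.

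The same row may be added in SAP 13.1.7 for CGI-I, using observed CGI-I scores where they exist. This would be for completeness and not to correct a known bias.

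The cost is a sentence or two in the SAP, one entry in SAP 18 and one extra table row (two if CGI-I is included), with no new data. The downside is a conservative response rate that may be slightly lower than the FAS figure. If every treated subject has a post-Baseline total, the added HAMD-17 row will equal the imputed FAS row.
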